7.2.1. Summaries of Numeric Laboratory Results

Descriptive statistics will be provided by cohort for each laboratory test specified in the study protocol as follows:

- Baseline values
- Values at each postbaseline time point
- Change and percent change from baseline at each postbaseline time point

A baseline laboratory value will be defined as the last measurement obtained on or prior to the date/time of first dose of study drug. Change from baseline to a postbaseline visit will be defined as the visit value minus the baseline value. The mean, median, Q1, Q3, minimum, and maximum values will be displayed to the reported number of digits; StD values will be displayed to the reported number of digits plus 1.

7.2.2. Graded Laboratory Values

The CTCAE Version 5.0 will be used to assign toxicity grades (0 to 4) to laboratory results for analysis. Grade 0 includes all values that do not meet the criteria for an abnormality of at least Grade 1. For laboratory tests with criteria for both increased and decreased levels, analyses for each direction (i.e., increased, decreased) will be presented separately. Local labs will be graded based on the central lab normal ranges with in-house macro.

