## 4. STUDY PROCEDURES

All subjects must be dosed within 28 days of providing written informed consent. Unless otherwise specified, visit windows are within -1 and +2 days for the treatment schedule and  $\pm$  7 days for response assessments. Absolutely no waivers for subject eligibility will be permitted.

Samples for PK, ADA, and biomarker analyses will be collected according to the protocol schedule of assessments and are to be shipped to the Sponsor's designee. Otherwise, all other laboratory procedures are to be performed locally at each study site ([Table 2](#)).

The schedule of assessments for all subjects before implementation of PA5 is presented in [Table 2](#). The schedule of assessments for all subjects who continue treatment following implementation of PA5 is presented in [Table 3](#).

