### 6.2. Subject Inclusion Criteria

Subjects meeting all the following inclusion criteria at Screening will be eligible for participation in the study.

- 1) Female or male adults, > 18 years of age, who are able to understand and give written informed consent.
- 2) Subjects with the following histologically documented metastatic (M1, Stage IV) or locally advanced solid tumors.
  - a) NSCLC (adenocarcinoma or SCC) that has progressed after prior platinum-based chemotherapy and programmed death-(ligand) 1 (PD-(L)1) directed therapy given sequentially (in either order) or in combination. These agents could have been taken as monotherapy or in combination with other agents. If subjects have had recurrence/relapse or lack of response within 6 months of completing chemotherapy with or without PD-(L)1 directed therapy for locally advanced disease, that line of therapy may be counted for eligibility.
  - b) HNSCC that has progressed after prior platinum-based chemotherapy and anti-PD-(L)1 directed therapy given sequentially (in either order) or in combination. These agents could have been taken as monotherapy or in combination with other agents. No more than 3 prior lines of systemic treatment is allowed.

- c) Endometrial carcinoma that has progressed after prior platinum-based chemotherapy and anti-PD-(L)1 directed therapy given sequentially (in either order) or in combination. These agents could have been taken as monotherapy or in combination with other agents. No more than 3 prior lines of systemic treatment is allowed. Endometrial carcinoma with any histology including MSI-h/dMMR and MSS are allowed.
- d) Extensive stage SCLC that has progressed after prior platinum-based chemotherapy and PD-(L)1 directed therapy. No more than one prior line of systemic treatment is allowed (re-challenge with the same initial regimen is not allowed).

- 3) ECOG Performance Status score of 0 or 1 (see Appendix [17.2](#)).
- 4) Adequate hematologic counts without transfusional or growth factor support within 2 weeks of study drug initiation (hemoglobin  $\geq$  9 g/dL, absolute neutrophil count (ANC)  $\geq$  1,500/mm^3, and platelets  $\geq$  100,000/ $\mu$ L).
- 5) Adequate hepatic function [bilirubin  $\leq$  1.5 institutional upper limit of normal (IULN), AST and ALT  $\leq$  2.5  $\times$  IULN or  $\leq$  5  $\times$  IULN if known liver metastases and serum albumin  $\geq$  3 g/dL].

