## 10. ASSESSMENT OF SAFETY

### 10.1. Safety Parameters

#### 10.1.1. Clinical Laboratory Investigations

All clinical laboratory samples for safety will be collected and analyzed by the site's local laboratory with appropriate clinical action taken based on the Investigator's clinical judgment. All investigations will be assessed for all subjects at Screening, during treatment, and upon treatment discontinuation per the schedule of assessments ([Table 2](#)). Clinical laboratory samples will also be collected at the 30-Day Safety Follow-up Visit. Additional and more frequent tests may be performed at the Investigator's discretion. The specific details of each assessment will be recorded on the appropriate eCRF. In the event of clinically significant abnormal results, tests should be repeated within 24 to 48 hours to confirm abnormality. Results for these laboratory tests should be followed until resolution. The panels of laboratory tests to be performed are shown below:

**Hematology:** hemoglobin, white blood cell (WBC) count and differential (with ANC), and platelet count.

**Clinical Chemistry:** total protein, albumin, total bilirubin, alkaline phosphatase (ALP), ALT, AST, creatinine (see [Appendix 17.3](#)) and clinical chemistries including glucose, sodium, potassium, magnesium, chloride, bicarbonate ( $\text{CO}_2/\text{HCO}_3^-$ ), calcium, phosphorus.

**Urinalysis:** performed locally on a freshly voided clean sample by dipstick for protein, glucose, blood, pH, and ketones. If dipstick findings are abnormal based on the Investigator's judgment, then a microscopic evaluation will be performed to assess the abnormal findings. Urinalysis will be performed at Screening only and as clinically indicated with details regarding casts, WBC count and RBC count, and bacteria recorded. Only abnormal results will be captured on the eCRF.

**Pregnancy and FSH Testing:** Female subjects of childbearing potential must have a negative serum or urine pregnancy test result within 72 hours prior to administration of the first dose of study drug and a negative urine pregnancy test result of Day 1 of every cycle while on study drug. If the urine test is positive or cannot be confirmed as negative, a serum pregnancy test will be required. Serum FSH testing will be conducted as needed per [Appendix 17.5](#) for determination of childbearing potential.

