1.1. Study Objectives and Endpoints

The objectives of this study are to evaluate the efficacy and the safety of sacituzumab govitecan in participants with metastatic solid tumors.

Primary Objective	Primary Endpoint
Efficacy	
Assess the ORR of sacituzumab govitecan in participants with metastatic solid tumors by Investigator's assessment according to the Response Evaluation Criteria in Solid Tumors Version 1.1 (RECIST v1.1) criteria.Objective response rate (ORR) according to RECIST v1.1 by Investigator's assessment.
Secondary Objectives	Secondary Endpoints
Efficacy/Safety/PK/ADA delineate objectives and endpoints	
Assess the ORR, duration of response (DOR), clinical benefit rate (CBR), and progression-free survival (PFS) of sacituzumab govitecan in participants with metastatic solid tumors by blinded independent central review (BICR) according to RECIST v1.1 criteria.Assess the DOR, CBR, and PFS of sacituzumab govitecan in participants with metastatic solid tumors by Investigator's assessment according to RECIST v1.1 criteria.ORR, DOR, CBR, and PFS according to RECIST v1.1 by BICR.DOR, CBR, and PFS, according to RECIS v1.1 by Investigator's assessment.Overall survival (OS).Incidence of treatment-emergent adverse events (AEs) and clinical laboratory abnormalities.Serum concentrations of sacituzumab govitecan over time and incidence of anti-drug antibody (ADA) to sacituzumab govitecan.

Assess the overall survival (OS) of sacituzumab govitecan in participants with metastatic solid tumors.Assess the safety of sacituzumab govitecan in participants with metastatic solid tumors.Assess the PK and immunogenicity of sacituzumab govitecan in participants with metastatic solid tumors.	
Exploratory Objectives	Exploratory Endpoints

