7.2.2.1. Treatment-Emergent Laboratory Abnormalities

Treatment-emergent laboratory abnormalities are defined as values that increase at least 1 toxicity grade from baseline at any postbaseline time point, up to and including the date of last dose of study drug plus 30 days or the day before initiation of subsequent anticancer therapy, whichever occurs first. If the relevant baseline laboratory value is missing, any abnormality of at least Grade 1 observed within the time frame specified above will be considered treatment emergent.

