7.2.4. Shifts Relative to the Normal Range

Shift tables will be presented by showing change in severity grade from baseline to the worst grade postbaseline for selected chemistry parameters (Creatinine/Glucose) and hematology parameters (Hemoglobin/Platelet Count/WBC count/Absolute neutrophil count).

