Appendix 3. Missing Data/Partial Dates Imputation Rules

Missing Data Imputation for Missing Date of Birth

The following conventions will be used for the imputation of date of birth when it is partially missing or not collected:

In general, age collected at Day 1 (the randomization date) (in years) will be used for analyses and presented in listings. If age at Day 1 is not available for a participant, then age derived based on date of birth and the Day 1 visit date will be used instead. If an enrolled participant was not dosed with any study drug, the randomization date will be used instead of the Day 1 visit date.

For screen failures, the date the first informed consent was signed will be used for the age derivation.

Missing normal ranges for laboratory parameters

When either the lower limit of normal, the upper limit of normal or both are missing or are not machine readable, a standardized reference range will be used.

Missing Data Imputation for Missing Adverse Event/Concomitant Medication Start Date

1) Missing day only

- If the month and year of the AE/the concomitant medication are the same as the month and year of the first dose date, the first dose date day will be used.
- • If the month and year are before the month and year of the first dose date, the first day of the month will be assigned to the missing day.
- • If the month and year are after the month and year of the first dose date, the first day of the month will be assigned to the missing day.

2) Missing day and month

- If the year is the same as the year of the first dose date, the first dose date day and month will be used.
- If the year is prior to the year of the first dose date, December 31 will be assigned to the missing fields.
- If the year is after the year of the first dose date, January 1 will be assigned to the missing fields.

3) Missing day, month, and year

- Uncertain: unable to impute.

The imputed start date should be prior or equal to the end date of the AE or medication. If only month is missing, then it will be imputed in a similar way as scenario 2) above. If both year and month missing and day not missing, then it will be imputed in a similar way as scenario 3) above.

Missing Data Imputation for Missing Adverse Event/Concomitant Medication Stop Date

4) Missing day only

- The month and year are the same as the month and year of the first dose date: use the last date of the month.

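### Does the SAP leave it unclear which normal range governs the grading of local laboratory results?

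*SAP*

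**What the plan says.** **Where samples are analysed.** Protocol 10.1.1: "All clinical laboratory samples for safety will be collected and analyzed by the site's local laboratory". Protocol section 4 sends out PK, ADA and biomarker samples, and otherwise "all other laboratory procedures are to be performed locally at each study site".

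**Which range grades the results.** SAP 7.2.2 uses CTCAE version 5.0 and adds: "Local labs will be graded based on the central lab normal ranges with in-house macro". It names no laboratory, range table or version.

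**What happens when limits are missing.** SAP Appendix 3 covers the case where the lower limit, the upper limit or "both are missing or are not machine readable, a standardized reference range will be used".

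**What depends on the grades.** SAP 7.2.2.1 defines treatment-emergent abnormalities as "values that increase at least 1 toxicity grade from baseline at any postbaseline time point", and SAP 7.2.4 has shift tables "showing change in severity grade from baseline to the worst grade postbaseline for selected chemistry parameters" and for some hematology counts. These outputs serve a secondary endpoint in SAP 1.1: "Incidence of treatment-emergent adverse events (AEs) and clinical laboratory abnormalities".

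**Eligibility.** Protocol 6.2, criterion 5, judges liver tests against the "institutional upper limit of normal (IULN), AST and ALT" limits of the site.

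**The concern.** Three features look wrong together.

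1. The central range has no visible owner. If every safety sample is analysed at the site, it is not obvious whose central range is meant.
2. A fallback for missing limits suggests that reported local limits are used when they are present. If 7.2.2 replaces every local range, the fallback has no work to do in grading. If local limits come first, 7.2.2 is wrong. Two programmers might then produce different tables.
3. A screening liver value is judged on the institutional limit for entry and on another range for its baseline grade.

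At stake are the laboratory grades for tests whose criteria are multiples of a normal limit. As an illustration with assumed ALT limits of 35 and 55 U/L, a result of 45 U/L is 45/35 = 1.29 times one limit (abnormal) and 45/55 = 0.82 times the other (normal). A grade can therefore depend on the choice of range, and with it whether a rise counts as treatment-emergent.

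**Working it through.** **Step 1. Do the two SAP rules conflict?** The plan gives no figure to reproduce, so this is a comparison of text.

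| Place | Subject | Range | Condition |
|---|---|---|---|
| SAP 7.2.2 | CTCAE grading of local results | central | none |
| SAP Appendix 3 | normal ranges with absent or unreadable limits | standardized | limits missing or unreadable |
| SAP 7.2 | flags in listings | the relevant one, not defined | none |
| Protocol 11.3 | share of subjects with abnormal values where CTCAE has no scale | not stated | no CTCAE scale |

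Only the first row concerns grading. Appendix 3 does not restrict itself to local limits and does not refer to grades. Rows three and four need normal limits for reasons other than grading: SAP 7.2 treats being outside the range and having a grade of 1 or more as separate triggers for a flag, and SAP 7.6 declares no departure from the protocol's safety analyses, so the Protocol 11.3 output stands. The Appendix 3 rule therefore has a use even if 7.2.2 governs all grading. A consistent reading exists, and it is the literal one.

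**Step 2. Is the eligibility contrast a defect?** Criterion 5 is a decision taken at one site before dosing. SAP 7.2.2 serves a summary pooled over sites. Nothing in the documents requires one range for both, and no visible analysis compares them. The shift tables do not include liver tests: SAP 7.2.4 lists creatinine, glucose, hemoglobin, platelets, white cells and neutrophils.

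**Step 3. How much could the range matter?** The documents give no ranges, so every input here is assumed.

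- Baseline *b*, in multiples of the local upper limit: lognormal, capped at 5. Peak *p* = *b* × a lognormal factor, not below 0.7*b*.
- Scenarios (baseline median, log-SD; factor median, log-SD): A (0.5, 0.5; 1.2, 0.4), B (0.5, 0.45; 1.4, 0.45), C (0.6, 0.5; 1.8, 0.6).
- *r* = local limit / common limit. On the common range, a participant is treatment-emergent if *rb* ≤ 1 and *rp* > 1 (one cut at 1 × the upper limit). On the local range, *r* = 1.
- 1,000,000 draws per scenario.

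| | A | B | C |
|---|---|---|---|
| Rate on local range | 14.4% | 23.4% | 40.0% |
| *r* uniform 0.9 to 1.1: status changed | 3.0% | 3.5% | 4.2% |
| change in rate (points) | -0.04 | -0.08 | -0.18 |
| *r* uniform 0.8 to 1.2: status changed | 5.6% | 6.9% | 8.3% |
| change in rate (points) | -0.3 | -0.4 | -0.8 |
| All sites at 0.8: change in rate (points) | -4.5 | -7.1 | -3.9 |
| All sites at 1.2: change in rate (points) | +3.2 | +4.6 | -0.4 |

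A repeat run moves these by about 0.1 point. In cohorts of 30 to 40 (SAP 1.3), the participants reclassified for one test number from 0.030 × 30 = 0.9 to 0.083 × 40 = 3.3. Changes go both ways, so the expected rate hardly moves. Shifts of several points need all sites on one side of the common range, and nothing in the documents shows that. The simulation covers upper limits only; no case with a lower limit was run.

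**The case for a change.** The best case for a change is traceability. Laboratory abnormalities are a named secondary endpoint, and SAP 2.2 foresees regulatory and publication use. The input that decides a grade sits in a macro that the SAP does not describe. SAP 7.2, 7.2.2 and Appendix 3 use three different terms for a range and define none. The protocol's only mention of central analysis of safety blood draws is in the contingency plan of Appendix 17.7, which names no laboratory and sits badly with sections 4 and 10.1.1. Naming the source and version would take a sentence or two.

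Part of this stands. The central range has no named referent in the visible text, and the terms could have been tied together. But this is missing detail, not a wrong or competing rule. The SAP leaves similar detail elsewhere: section 5.2.2 refers the reader to programming specifications for relative dose intensity. Those specifications are not available here, so their silence cannot be assumed.

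The larger remedies do not earn their place. Grading on each site's own range would drop a uniform rule, and the same absolute value could then be graded differently at different sites. It would also depend on local range data whose completeness is unknown. That is a trade-off, not a gain. A second tabulation on local ranges would add output to a descriptive summary whose expected rates barely move unless sites lie on one side.

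**Conclusion.** No change follows. The range for grading is stated in SAP 7.2.2, the Appendix 3 rule can stand beside it, and the institutional limit for eligibility serves another purpose. The unnamed source and version are a documentation gap that the programming team must fill in any case to run the macro.

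The reach is narrow: descriptive summaries of laboratory grades, and only for criteria set relative to a normal limit. Which tests those are is an assumption, because the documents do not reproduce CTCAE. Criteria on absolute values, adverse events graded by the investigator (SAP 7.1.2) and the response rate are unaffected, and SAP 7.2 lists individual laboratory values by participant. The true size cannot be computed from the documents. The illustration, less than 1 point in the expected rate and about 1 to 3 participants reclassified per test and cohort, rests on assumed distributions and on site limits spread around the common one. The conclusion would need another look if site limits were found to lie mostly on one side of it.

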7.2.2.1. Treatment-Emergent Laboratory Abnormalities

Treatment-emergent laboratory abnormalities are defined as values that increase at least 1 toxicity grade from baseline at any postbaseline time point, up to and including the date of last dose of study drug plus 30 days or the day before initiation of subsequent anticancer therapy, whichever occurs first. If the relevant baseline laboratory value is missing, any abnormality of at least Grade 1 observed within the time frame specified above will be considered treatment emergent.

7.2.2.2. Summaries of Laboratory Abnormalities

The following summaries (number and percent of participants) for treatment-emergent laboratory abnormalities will be provided by lab test and cohort; participants will be categorized according to the most severe postbaseline abnormality grade for a given lab test:

- TE laboratory abnormalities
- Grade 3 or 4 laboratory abnormalities

For all summaries of laboratory abnormalities, the denominator is the number of participants in the Safety Analysis Set with non-missing postbaseline values.

A by-participant listing of treatment-emergent Grade 3 or 4 laboratory abnormalities will be provided by participant ID number and time point in chronological order. This listing will include all test results that were collected throughout the study for the lab test of interest, with all applicable severity grades displayed.

7.2.3. Liver-related Laboratory Evaluations

Liver function abnormalities after initial study drug administration will be examined and summarized for selected chemistry and hematology parameters.

7.2.4. Shifts Relative to the Normal Range

Shift tables will be presented by showing change in severity grade from baseline to the worst grade postbaseline for selected chemistry parameters (Creatinine/Glucose) and hematology parameters (Hemoglobin/Platelet Count/WBC count/Absolute neutrophil count).

7.3. Body Weight, Height, and Vital Signs

During treatment, participant's body weight will be measured at Screening, on Day 1 of each treatment cycle (or more frequently if the participant's body weight changed by > 10% since the previous administration), at the end of treatment (EOT) Visit, and at the 30-Day Safety Follow-up Visit. Participant's height will only be measured at Screening.

Vital sign measurements (systolic blood pressure, diastolic blood pressure, heart rate, respiratory rate, and body temperature) will be taken at the Screening/Baseline visit (within 28 days of C1D1), C1D1 prior to infusion and other timepoints during the study if clinically indicated.

All the collected information will be presented for each participant in a by-participant data listing.

7.4. Electrocardiogram Results

The standard 12-lead electrocardiogram (ECG) will be obtained at the Screening/Baseline visit (within 28 days of C1D1), C1D1 prior to infusion, and repeated during the study if clinically indicated.

As ECG comments were collected as free text field, a listing will be produced for ECG parameters along with any investigator comments that may be provided.

7.5. Other Safety Measures

No additional safety measures are specified in the protocol.

7.6. Changes From Protocol-Specified Safety Analyses

There are no deviations from the protocol-specified safety analyses.

8. PHARMACOKINETIC (PK) AND IMMUNOGENICITY ANALYSES

8.1. Pharmacokinetics Analyses

Descriptive summary of PK concentration (SG, free SN-38 and total antibody - hRS7 IgG) and PK parameters will be summarized by visits. A listing of PK concentrations will also be provided. Participants in the PK population will be included for analyses.

Pharmacokinetics analyses including population pharmacokinetics (PopPK), exposure-efficacy and exposure-safety analyses will be described in separate analyses plans.

Data from this study may be combined with data from other studies for PopPK and exposure response analyses. If applicable, results from such analyses may be summarized in a separate report, rather than in a CSR.

